6. GENERAL ANALYSIS DEFINITIONS

6.1 TREATMENT(S)

There will be 5 treatment phases in this trial: screening period, placebo run-in period, double-blind treatment period (with either BI drug or matching placebo), post-treatment and post-study.

Table 6.1: 1 Treatment regimens / study intervals

| Label | Interval | Start date | Start time |
|------------------------|----------------------------------|--|---|
| Screening | Screening period | Date of informed consent | 00:00 |
| Run-in Placebo | Placebo run-in period | Date of first administration of run-in medication | 00:00 |
| Lina 5 mg / Placebo | Double-blind treatment period | Date of first administration of study medication for double-blind treatment period | Time of first administration of study medication, 12:00 if missing |
| Post-treatment | Post-treatment | Date of last drug intake + X* + 1 | 00:00 |
| Post-study | Post-study | Date of last contact + 1 | 00:00 |

* The endpoint specific follow-up period for the assignment to active treatment are presented in detail in [Section 6.7](#).

The purpose of the definition in the above is to describe all the different study/treatment intervals, in which a patient can lie during the course of the trial. Note that the term “treatment regimen” can also cover time periods with no active treatment.

The efficacy and safety analyses will follow the intention-to-treat (ITT) principle in assigning patients to treatment groups, i.e. patients will be analysed as randomised.

If a patient erroneously receives the wrong trial drug, the patient will be analysed ‘as randomised’. Additionally, the AEs with an onset during the time of the incorrect study treatment will also be listed separately.

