16.1.9 Documentation of statistical methods

Proprietary confidential information © 2019 Boehringer Ingelheim International GmbH or one or more of its affiliated companies

Boehringer Ingelheim

TSAP for BI Trial No: 1218.102

Page 26 of 47

Proprietary confidential information © 2019 Boehringer Ingelheim International GmbH or one or more of its affiliated companies

Missing dates and times

Missing or partial date and time information for AEs will be replaced according to general BI rules (2).

If the date of first drug administration is missing but the patient was randomised and treated, the date of the first drug administration will be set to the date of randomization. If the date of first administration is partially missing with the month and year present, the day will be set to the date of randomization if randomisation was in the same month. If randomization was in the month prior to the first drug administration the missing day will be imputed as the first day of the month. A missing time of first drug administration will be imputed as 12:00 o'clock noon, missing administration times at on-treatment visits will be imputed by 8:00 o'clock in the morning.

As a general rule, a missing drug stop date will be imputed according to the following principles:

- If an End of Treatment (EoT) visit is documented, it should be the date of the EoT visit.
- If the date is incomplete with only month and year and the EoT visit is missing, it should be the first day of the following month.
- If the patient is lost to follow-up it should be the date of the last visit + the longest treatment duration based on drug supply + 1 day.
- All other cases need to be assessed by the trial team on an individual basis, trying to use the points above as guidance.

Additional rules for the treatment set-up in O*C:

- Since usually no times are available for the start of the screening, placebo run-in period will be considered to start at 0:00 o'clock (midnight).
- Also the start of the post-treatment period will be considered at 0:00 o'clock (midnight) on the day after the study drug stop date.
- The post study period on the date after the follow-up visit, starting at 0:00 o'clock midnight.

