- In general, the start of the post-treatment period is defined as date of last drug administration + 1 day. If the drug stop date is incomplete with only month and year present, the post-treatment period starts on the first day of the following month (i.e. at the same day as the imputed drug stop date).
- The post study period start is intended to start on the date of last contact + 1 day and the date of last contact is assumed to be after the date of last drug administration. In patients who discontinue the study, it can happen that the date of last contact is before date of last drug administration. To account for such cases the start of the post-study

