16.1.9 Documentation of statistical methods

Proprietary confidential information © 2019 Boehringer Ingelheim International GmbH or one or more of its affiliated companies

Proprietary confidential information © 2019 Boehringer Ingelheim International GmbH or one or more of its affiliated companies

period is defined as the maximum of the last contact date + 1 day, the date of the last visit + 1 day and the start of the post-treatment period + 1 day.

Only the year of birth will be collected in the eCRF, and the day and month of birth will be imputed as 01 January. For other incomplete date information always the midpoint of the possible interval will be used. If only the year is present, the day and month will be imputed as 01 July, if year and month is present the day will be imputed. If the year is missing, the date will be considered missing.

If this leads to contradictions for the start or end date of a concomitant therapy (e.g. imputed end date before documented start date), a partial end date will be imputed as the end of the interval or a partial start date will be imputed as the start of the interval in the database to resolve this contradiction.

Missing dates for meal tolerance test in the eCRF should be replaced based on the dates of the according lab samples. Missing times for the start and end of a meal will not be imputed.

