16.1.9 Documentation of statistical methods

Proprietary confidential information © 2019 Boehringer Ingelheim International GmbH or one or more of its affiliated companies

Boehringer Ingelheim

TSAP for BI Trial No: 1218.102

Proprietary confidential information © 2019 Boehringer Ingelheim International GmbH or one or more of its affiliated companies

Table 6.7: 1 Endpoint specific follow-up period for the assignment to active treatment

| Endpoint | Last day of assignment to treatment phase (days after study drug stop date) |
|---|--|
| Efficacy | |
| HbA _{1c} | 7 |
| FPG | 1 |
| PPG, | 0 |
| Body weight | 7 |
| Waist circumference | 7 |
| Rescue medication (new antidiabetic treatment, increases of background antidiabetic treatment) | |
| If patient did not prematurely discontinue from trial medication | -1 |
| If patient prematurely discontinued from trial medication (any reason) | 0 |
| Safety | |
| Adverse events | 7 |
| Safety laboratory measurements | 7 |
| Vital signs | 7 |

Measurements taken after the end of the follow-up period after the last intake of study drug will be considered post-treatment values.

On-treatment efficacy measurements will be assigned to visits based on time windows around the planned visit dates. These time windows are defined based on the planned number of days after the date of first administration of study drug (usually this is at Visit 3). Reasons to base the time windows on the actual treatment start date rather than the randomisation date are:

- If first intake of study drug shows a large delay by e.g. more than one week after the date of randomisation, a measurement taken four weeks after randomisation rather reflects the drug effect after three weeks than after four weeks and thus may underestimate the treatment effect at this visit.
- With large delays of the introduction of study drug after the randomization, the time window for the first on-treatment visit could include times the patients was not yet on study drug.

The time window for the first visit after randomization starts on the day after the first intake of study drug. This maximises the number of measurements used in by visit analyses and provides consistency with the planned last observation carried forward (LOCF) approach, but may lead to an underestimation of the treatment effect at the first visit form parameters that react slowly on treatment.

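### SAP 6.6 starts the post-treatment period one day after the last dose, while the SAP's own tables, its AE section and the protocol keep adverse events on treatment for seven days

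*SAP*

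**What the plan says.** SAP 6.6, in its additional rules for setting up treatment periods in Oracle Clinical, gives the start of post-treatment twice. One rule places it at midnight "on the day after the study drug stop date". A later one reads "In general, the start of the post-treatment period is defined as date of last drug administration + 1 day". Neither mentions an endpoint-specific follow-up period or makes an exception for adverse events.

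SAP Table 6.1:1 defines the same-named interval as starting at "Date of last drug intake + X* + 1" and refers to Section 6.7 for X. Table 6.7:1 gives X = 7 for adverse events, safety laboratory measurements and vital signs.

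Other places that support seven days:

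- SAP 6.6 itself, under safety and other variables, takes the last on-treatment safety value up to 7 days after drug stop.
- SAP 7.8.1 assigns adverse events through the 7-day residual effect period (REP) to the randomised treatment, assigns only later ones to post-treatment, and points to Section 6.1 for the definition.
- SAP 7.8.2 treats laboratory values up to 7 days after the last dose as on treatment.
- Protocol 3.1, 5.3.6.2 and 7.3.4 give the same 7 days for adverse events.

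Two linked rules in SAP 6.6 matter for the repair. The post-study period starts at the latest of three dates, one of which is "the start of the post-treatment period + 1 day"; Table 6.1:1 has simply "Date of last contact + 1". For a stop date with only month and year and no end-of-treatment visit, "it should be the first day of the following month", and post-treatment then starts "at the same day as the imputed drug stop date".

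**The concern.** The set-up rules are the text from which a programmer would build the treatment periods, and they disagree with the table that defines those periods. Followed literally, they would class adverse events starting in the first week after the last dose as post-treatment.

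Under SAP 7.8.1 the in-text adverse event tables show only events assigned to randomised treatment, and the end-of-text tables show post-treatment events pooled over the arms. The comparison between linagliptin and placebo would be lost for these events. Protocol 3.2 says that the pharmacodynamic effect lasts about 7 days after the last dose, so this is a week in which drug effect is still expected.

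**Working it through.** Let D be the day of the last dose.

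**Boundary by endpoint.** SAP 6.6 gives D + 1 throughout. Table 6.1:1 gives D + X + 1, with X from Table 6.7:1.

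| Endpoint | X | Table 6.1:1 | SAP 6.6 | Difference (days) |
|---|---|---|---|---|
| Adverse events, safety laboratory, vital signs | 7 | D+8 | D+1 | 7 |
| HbA1c, body weight, waist circumference | 7 | D+8 | D+1 | 7 |
| FPG | 1 | D+2 | D+1 | 1 |
| PPG; rescue medication after premature discontinuation | 0 | D+1 | D+1 | 0 |
| Rescue medication, no premature discontinuation | −1 | D | D+1 | −1 |

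The two rules agree only where X = 0. For example, with a last dose on 15 June, adverse events become post-treatment on 16 June under 6.6 and on 23 June under the tables. Onset on or before D, or from D+8 on, is classed alike; only D+1 to D+7 differs.

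**Scale.** Table 6.7:2 puts Visit 8 on treatment day 169, and protocol 5.2 has a dose of study medication given at that visit. A completer's planned adverse event window is 169 + 7 = 176 days, and 7/176 = 3.98%. This is a share of time, not an estimate of affected events.

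**Effect on the post-study rule.** Let the last contact be on D+k, with no later visit.

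- Present 6.6 rule: max(D+k+1, D+2). A completer contacted on D+7 starts post-study on D+8, as Table 6.1:1 gives.
- Post-treatment moved to D+8, with the extra day in the guard kept: max(D+k+1, D+9). The same completer moves to D+9, which no longer matches Table 6.1:1.
- Extra day removed: max(D+k+1, D+8). The completer stays on D+8.

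Compared with the present rule, the last version moves post-study by 0 days for k ≥ 7, by 1, 2, 3, 4 and 5 days for k = 6, 5, 4, 3 and 2, and by 6 days for k ≤ 1. An early discontinuer who attends Visit 8 within 7 days of stopping and Visit 9 seven days later (protocol 6.2.2) has k between 7 and 14, so nothing moves.

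**Stop date known only to the month.** For June with no end-of-treatment visit, the stop date is imputed as 1 July. Taken as the stop date, it gives 1 July + 7 + 1 = 9 July for adverse events. If the imputed date already contains the one-day step (latest possible stop 30 June), it gives 30 June + 7 + 1 = 8 July. The SAP does not say which applies once the 7 days are added.

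**The case against.** The strongest reply is that assignment of adverse events is already settled. SAP 7.8.1 states the rule outright and refers to Section 6.1, and every other relevant passage agrees. A programmer would have to work against a specific instruction to go wrong. This stands, and it limits the point to a risk of misprogramming.

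A second reply is that the 6.6 bullets are general set-up rules, placed under missing dates and times. They may describe a base interval in the database to which endpoint lags are added at analysis. That is plausible, since X differs by endpoint. But the SAP says this nowhere, and Table 6.1:1 defines an interval of the same name with X built in.

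A third reply is that one set-up rule cannot carry a single X. That is correct, and the repair has to name the endpoint that each X serves. A bare pointer from 6.6 to the tables would settle adverse events but leave two definitions under one name.

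**Conclusion.** The 6.6 wording does not match the SAP's own definition and should be corrected. The boundary for adverse events is 7 days too early, 4.0% of a completer's planned window. Harm follows only if the set-up was built literally from 6.6, which the documents do not show. It would reach descriptive safety tables only. Severity: minor.

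A reader might infer more, but the documents do not support it:

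- **Efficacy data would be lost too.** SAP 6.7 assigns measurements by its own endpoint-specific windows, so HbA1c and the primary analysis do not depend on the 6.6 rule. Power is likewise untouched.
- **SAP 6.6 contradicts itself for a stop date known only to the month.** That sentence is worded as an explicit exception to the general rule, and it makes sense if the imputed date already includes the extra day. What is missing is how the 7 days are then counted.
- **Hypoglycaemia is especially exposed because home testing becomes daily in follow-up.** Scheduled tests are not events, and symptom-triggered testing applies throughout (protocol 5.3.5), so test frequency does not measure the number of affected events.
- **Protocol 5.3.6.2 cuts short event collection in early discontinuers.** That concerns collection, not assignment, and it depends on a figure that is not shown in the text available.

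**What to change.** 1. In both SAP 6.6 statements, replace the one-day rule with that of Table 6.1:1. Adverse event assignment then uses last drug intake + 7 + 1, and other endpoints use their own X from Table 6.7:1.
2. Reword the post-study guard in 6.6 so that, for adverse events, post-study does not start before the 7-day REP has ended, and drop its extra day. A completer contacted on day 7 then still starts post-study on day 8, as in Table 6.1:1.
3. For a stop date known only to the month, state whether the imputed first of the following month already contains the one-day step before the 7 days are added.

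The cost is SAP wording, with no new data. The one knock-on is that patients last contacted before day 7 start post-study 1 to 6 days later than now, with an empty post-treatment interval. Table 6.1:1 already gives an empty interval for a completer contacted on day 7.

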16.1.9 Documentation of statistical methods

Proprietary confidential information © 2019 Boehringer Ingelheim International GmbH or one or more of its affiliated companies

Proprietary confidential information © 2019 Boehringer Ingelheim International GmbH or one or more of its affiliated companies

period is defined as the maximum of the last contact date + 1 day, the date of the last visit + 1 day and the start of the post-treatment period + 1 day.

Only the year of birth will be collected in the eCRF, and the day and month of birth will be imputed as 01 January. For other incomplete date information always the midpoint of the possible interval will be used. If only the year is present, the day and month will be imputed as 01 July, if year and month is present the day will be imputed. If the year is missing, the date will be considered missing.

If this leads to contradictions for the start or end date of a concomitant therapy (e.g. imputed end date before documented start date), a partial end date will be imputed as the end of the interval or a partial start date will be imputed as the start of the interval in the database to resolve this contradiction.

Missing dates for meal tolerance test in the eCRF should be replaced based on the dates of the according lab samples. Missing times for the start and end of a meal will not be imputed.

6.7 BASELINE, TIME WINDOWS AND CALCULATED VISITS

With regard to efficacy and safety endpoints, the term “baseline” generally refers to the last observed measurement prior to administration of any randomised study medication. For daily insulin dose the baseline will be derived from the eCRF and is equal to the daily insulin dose at day of first study medication intake. Also, for metformin, baseline dose refers to the dose at day of first study medication intake.

Measurements taken prior to the first intake of randomised study drug will be considered pre-treatment values. The pre-treatment values will be assigned to a visit according to the nominal visit number as recorded on the eCRF or as provided by the laboratory.

The date and clock time of the first drug administration will be used to separate pre-treatment from on-treatment values. Measurements taken after the first intake of randomised study drug will be considered on-treatment values if they have been obtained up to end of the parameter specific follow-up period as defined in Table 6.7: 1 below and will be assigned to the randomised study drug for analyse.

16.1.9 Documentation of statistical methods

Proprietary confidential information © 2019 Boehringer Ingelheim International GmbH or one or more of its affiliated companies

Boehringer Ingelheim

TSAP for BI Trial No: 1218.102

Proprietary confidential information © 2019 Boehringer Ingelheim International GmbH or one or more of its affiliated companies

Table 6.7: 1 Endpoint specific follow-up period for the assignment to active treatment

| Endpoint | Last day of assignment to treatment phase (days after study drug stop date) |
|---|--|
| Efficacy | |
| HbA _{1c} | 7 |
| FPG | 1 |
| PPG, | 0 |
| Body weight | 7 |
| Waist circumference | 7 |
| Rescue medication (new antidiabetic treatment, increases of background antidiabetic treatment) | |
| If patient did not prematurely discontinue from trial medication | -1 |
| If patient prematurely discontinued from trial medication (any reason) | 0 |
| Safety | |
| Adverse events | 7 |
| Safety laboratory measurements | 7 |
| Vital signs | 7 |

Measurements taken after the end of the follow-up period after the last intake of study drug will be considered post-treatment values.

On-treatment efficacy measurements will be assigned to visits based on time windows around the planned visit dates. These time windows are defined based on the planned number of days after the date of first administration of study drug (usually this is at Visit 3). Reasons to base the time windows on the actual treatment start date rather than the randomisation date are:

- If first intake of study drug shows a large delay by e.g. more than one week after the date of randomisation, a measurement taken four weeks after randomisation rather reflects the drug effect after three weeks than after four weeks and thus may underestimate the treatment effect at this visit.
- With large delays of the introduction of study drug after the randomization, the time window for the first on-treatment visit could include times the patients was not yet on study drug.

The time window for the first visit after randomization starts on the day after the first intake of study drug. This maximises the number of measurements used in by visit analyses and provides consistency with the planned last observation carried forward (LOCF) approach, but may lead to an underestimation of the treatment effect at the first visit form parameters that react slowly on treatment.

16.1.9 Documentation of statistical methods

Proprietary confidential information © 2019 Boehringer Ingelheim International GmbH or one or more of its affiliated companies

Boehringer Ingelheim

TSAP for BI Trial No: 1218.102

Proprietary confidential information © 2019 Boehringer Ingelheim International GmbH or one or more of its affiliated companies

The midpoint between two on-treatment visits defines the end of a time window, with the midpoint being included in the time window of the preceding visit. The end of the time window of the last on-treatment visit (EoT) is endpoint dependent (cf. [Table 6.7: 1](#)).

Table 6.7: 2 Time windows for on-treatment efficacy measurement scheduled for each on-treatment visit

| Visit number | Visit label | Planned days after randomisation | Planned days on treatment | Time window (actual days on treatment) | |
|--------------|-------------|----------------------------------|---------------------------|--|-------------------------------|
| | | | | Start | End ^A |
| 3 | Baseline | 0 | 1 | NA | 1 ^B |
| 4 | Week 4 | 28 | 29 | 2 | 43 |
| 5 | Week 8 | 56 | 57 | 44 | 71 |
| 6 | Week 12 | 84 | 85 | 72 | 106 |
| 7 | Week 18 | 126 | 127 | 107 | 148 |
| 8 | Week 24/EoT | 168 | 169 | 149 | Study drug stop date + X days |

^A In case of premature discontinuation of the study drug a Visit 8 (EoT) has to be performed. If such a Visit 8 falls into the time window of a previous visit, measurements will be assigned to this previous visit and the visit value will be determined as described below. In this case the time window for the visit that includes Visit 8 will end X days after the study drug stop date, including Day X. The definition of X is endpoint specific, cf. [Table 6.7: 1](#).

^B Only values taken prior to the start of treatment with randomised study drug can be considered baseline values. Time windows will be used for assignment of measurements to scheduled visits.

For examinations that are not planned at every on-treatment visit, the time windows will be defined according to the same algorithm, based on the midpoint between the planned visit day of such an examination.

Repeated and unscheduled efficacy measurements will be assigned to the nominal visits and listed in the subject data listings according to the time windows described above. Only one observation per time window will be selected for analysis at an on-treatment visit – the value will be selected which is closest to the protocol planned day. If there are two observations which have the same difference in days to the planned day or if there are two observations on the same day, the earliest value will be used. If an observation is available on the last day of treatment, this observation will be preferably selected over any later observation that is still within the time window. If there are multiple values within the time window of the last visit, including a value on the last day of drug intake, the value on the last day of drug intake is used as the value of the last visit.

Safety measurements will be assigned to the nominal visit as recorded on the eCRF or as provided by the laboratory.

